Appendix D: PSV Ventilation Strategy

INITIATION OF PSV

Assess at least once daily while on A/C for Criteria for Switching from A/C to PSV

Ventilator Settings:
 PS level: 10-20 cmH₂O or at previous level
 Inspiratory trigger: per clinician
 Expiratory trigger: 25% of peak flow_i
 PEEP: at previous level
 FiO₂: at lowest level required to keep SpO₂ 90-96%

Alarm Settings:
 Paw max: per clinician
 RR max: 38 b/min
 Vte max: 12 mL/kg of PBW
 Vte min: 0 mL
 VE max: 20 L/min
 VE min: 5 L/min
 Apnea setting: 20 s

ALGORITHM TO ADJUST PSV BASED ON CLINICAL PARAMETERS

Assess at least every 8 hours while on PSV to determine if adjustments are needed to maintain Target Range

**Repeat blood gas q 30 min as needed to confirm pH 7.32-7.47*

†Best clinical judgement should always prevail in setting of deterioration, with frequent reassessment until stable

```

    graph TD
      Start[No Respiratory Distress:  
Patient appears comfortable  
RR 12-35 and Vte 5-10 mL/kg PBW] --> Target[Target range achieved.  
No adjustments required unless one of the following occurs:]
      Target --> RR[Vte <5 or >10 mL/kg PBW:  
Obtain arterial blood gas.  
No adjustments required unless:]
      RR --> Alk[Respiratory alkalemia]
      RR --> Acid[Respiratory acidemia or  
Respiratory Distress  
(see definition)]
      Alk --> Hypervent[Treat any apparent cause of hyperventilation  
(eg. Pain, anxiety, metabolic acidosis)]
      Hypervent --> DecreasePSV[Decrease PS in steps of 2-3 cmH2O until  
Vte <8 mL/kg PBW and/or pH ≤ 7.47]
      Acid --> IncreasePSV[Increase PS in steps of 2-3 cmH2O until  
respiratory distress resolves and pH ≥ 7.32  
(confirm with repeat blood gas*)]
      IncreasePSV --> SwitchA/C[Switch to A/C mode if ≥ 1 of:  
PS >20 cmH2O  
PS + PEEP > 30 cmH2O  
FiO2 >60% required for SpO2 ≥90%  
Clinical instability (see definition)†  
Unable to trigger vent (NMB/sedation)]
      SwitchA/C --> Reassess[Reassess within 24 hours for Criteria for  
Switching from A/C to PSV]
      Start --> Distress[Respiratory Distress with ≥2 signs:  
See definition]
      Distress --> TreatCause[Treat any apparent cause of respiratory distress  
(eg. secretions, bronchospasm, pulmonary edema)]
      TreatCause --> IncreaseFiO2[Increase FiO2 and/or PEEP as needed to  
keep SpO2 >90%]
      IncreaseFiO2 --> IncreasePSV
  
```

ALGORITHM FOR WEANING

Assess at least once daily while on PSV for Criteria to Initiate Weaning; Attempt to wean FiO₂ to 0.40 and PEEP to ≤8 cmH₂O

```

    graph LR
      Start[Criteria to Initiate Weaning:  
SpO2 ≥90%  
FiO2 ≤0.40  
PEEP ≤8 cmH2O  
pH ≥ 7.32  
vasopressors no higher than  
norepinephrine 0.1 µg/kg/min] --> PreSBT[Pre-SBT readiness assessment:  
CPAP 0 cmH2O and  
FiO2 0.40 for 2 min;  
assess f/Vt]
      PreSBT --> fVt1[f/Vt <100]
      PreSBT --> fVt2[f/Vt ≥100]
      fVt1 --> SBT[SBT: t-piece,  
FiO2 0.40 for 30 min]
      SBT --> PassSBT[Pass SBT:  
assess for extubation]
      fVt2 --> ReturnPSV[Return to PSV  
Reassess within 24 hr]
      PassSBT --> FailSBT[Fail SBT]
      ReturnPSV --> FailSBT
      FailSBT --> ReturnPSV
  
```

Appendix E: Richmond Agitation Sedation Scale (RASS)

C. Sessler, M. Gosnell, M. Grap, G. Brophy, P. O'Neal, K. Keane, E. Tesoro, R. Elswick. "The Richmond Agitation–Sedation Scale", *Am. J. Respir. Crit Care Med*, vol. 166, no. 10 (2002), pp. 1338-1344.

Score	Term	Description
+4	Combative	Overtly combative, violent, immediate danger to staff
+3	Very Agitated	Pulls or removes tube(s) or catheter(s) or has aggressive behavior toward staff
+2	Agitated	Frequent nonpurposeful movement or patient-ventilator dyssynchrony
+1	Restless	Anxious but movements not aggressive or vigorous
0	Alert and Calm	
-1	Drowsy	Not fully alert, but has sustained (> 10 seconds) awakening, with eye contact, to voice
-2	Light Sedation	Any movement (but no eye contact) to voice
-3	Moderate Sedation	Movement or eye opening to voice (but no eye contact)
-4	Deep Sedation	No response to voice, but any movement to physical stimulation
-5	Unarousable	No response to voice or physical stimulation

Procedure

1. Observe patient. Is patient alert and calm (score 0)?

Does patient have behavior that is consistent with restlessness or agitation (score +1 to +4 using the criteria listed above, under description)?

2. If patient is not alert, in a loud speaking voice state patient's name and direct patient to open eyes and look at speaker. Repeat once if necessary. Can prompt patient to continue looking at speaker.

Patient has eye opening and eye contact, which is sustained for more than 10 seconds (score –1).

Patient has eye opening and eye contact, but this is not sustained for 10 seconds (score –2).

Patient has any movement in response to voice, excluding eye contact (score –3).

3. If patient does not respond to voice, physically stimulate patient by shaking shoulder and then rubbing sternum if there is no response to shaking shoulder.

Patient has any movement to physical stimulation (score –4).

Patient has no response to voice or physical stimulation (score –5).

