Different scoring systems were used across institutions to assess the level of sedation or agitation and included the Richmond Agitation Scalation Score (RASS), the Riker Sedation-Agitation Scale (SAS), or the Ventilator-Adjusted Motor Activity Assessment Scale (VA-MAAS). Sedation was scored twice daily (morning score and highest daily score) using whatever scale was in use at each participating centre. Each score will be analyzed separately, and scores will be converted to 4 categories using the following conversion table derived from Khan et al 2012[29], and analyzed descriptively.

Category	RASS	VAMASS	SAS
Moderate to deep sedation	-3 to -5	0 to 1	1-2
Light sedation	-2 to -1	2	3
Alert and calm	0	3	4
Restless/Agitated	+1 to +4	4 to 6	5 to 7

Delirium score

Delirium category will be assessed in a subset of patients where data is available using a combination of two scoring systems: the Confusion Assessment Method for the ICU (CAM-ICU) and the Intensive Care Delirium Screening Checklist (ICDSC) values as follows:

- 1. Delirium not assessed: either missing data or marked as not assessed in database
- 2. Too sedated to assess = Coma
- 3. Delirious (CAM-ICU positive, ICDSC 4-8)
- 4. Not delirious (CAM-ICU negative, ICDSC 0-3)

The delirium category will be described over the study period for each group.

6 Analysis methods: Frequentist Analysis

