6.4 Covariates of Interest

The following were pre-specified as covariates are of particular interest

- 1. Duration of mechanical ventilation prior to randomization in 1) days and 2) as a binary indicator for greater than 5 days or not.
- 2. 2. Failed spontaneous breathing trial (SBT) vs. failed continuous positive airway pressure (CPAP) zero trial (CPAP trial of 0 cmH2O) vs. failed weaning criteria prior to randomization
- 3. Failed extubation prior to randomization (Failed extubation vs. No extubation attempt prior to randomization)
- 4. Mild, moderate, severe frailty assessed using the Clinical Frailty Scale (CFS) [30]. There should not be anyone with CFS 9 (Terminally ill) in the study based on the inclusion criteria

- Mild: CFS 1 to 3 (very fit to managing well)
- Moderate: CFS 4 to 6 (managing well to mildly frail)
- Severe: CFS 7 to 8 (severely frail to very severely frail)

In addition to the above pre-specified covariates, we will explore the effects of baseline cumulative fluid balance and baseline sedation category in adjusted analyses. In addition, baseline use of antipsychotics, neuromuscular blockers and steroids will be described.

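### The RASS table in Protocol Appendix E conflicts with its own scoring procedure at -2 versus -3, the line where the SAP divides light from moderate-to-deep sedation

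*Protocol*

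**What the plan says.** Protocol Appendix E has two parts: a table with a description for each RASS score, and a stepwise procedure for assigning the score. In the table, -2 is "Any movement (but no eye contact) to voice". In step 2 of the procedure, -2 applies when "Patient has eye opening and eye contact, but this is not sustained for 10 seconds", and -3 applies when "Patient has any movement in response to voice, excluding eye contact".

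Protocol 8.4.1 refers to Appendices E and F for how to assess RASS and SAS. It also asks research personnel to score one of the two at least once a day in centres that do not routinely chart a validated scale.

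SAP 5.5.2 converts RASS, SAS and VA-MAAS scores to four categories. RASS -1 and -2 count as light sedation; the next category is "Moderate to deep sedation -3 to -5". The categories are to be analysed descriptively. SAP 4.7 lists baseline sedation category among the baseline characteristics, and SAP 6.4 says the trial will explore the effects of "baseline cumulative fluid balance and baseline sedation category in adjusted analyses".

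**The concern.** The two halves of one appendix disagree about what separates -2 from -3. The procedure uses eye contact: brief contact is -2, none is -3. The table says there is no eye contact at either score, so it hardly separates them.

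This would be a small matter if both scores fell in one analysis category. They do not: the SAP places its cut between them. A response that the procedure places in the moderate-to-deep category can therefore be recorded as light sedation by someone reading the table. Whether sedation scores differ between arms is one of the research questions in SAP 1.1, and the daily scores appear again in SAP 6.2, so these data will be reported.

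**Working it through.** No arithmetic applies. The check sets the two parts of Appendix E beside the SAP categories.

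| Score | Appendix E, table | Appendix E, procedure step 2 | SAP 5.5.2 category |
|---|---|---|---|
| -1 | "Not fully alert, but has sustained (> 10 seconds) awakening, with eye contact, to voice" | Eye contact held for more than 10 seconds | Light |
| -2 | Movement to voice, no eye contact | Eye contact, held for less than 10 seconds | Light |
| -3 | "Movement or eye opening to" voice, no eye contact | Movement to voice, no eye contact | Moderate to deep |

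Two kinds of patient show the consequence.

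1. *Moves to voice, no eye contact.* The table allows -2 or -3, because its -3 row differs only by adding eye opening. The procedure allows only -3. The SAP category is light if the rater takes the table's -2 row, and moderate to deep under the procedure.
2. *Brief eye contact to voice.* No table row fits: -1 needs sustained contact, and -2 and -3 both exclude contact. The procedure gives -2. A rater forced to choose -1 or -2 from the table still lands in light sedation. Only a choice of -3 would change the category, and that row also excludes eye contact.

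The clear route to a changed category is therefore the first, from moderate to deep into light.

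Next, where the -2/-3 line is used:

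- **Primary analysis (SAP 6.1).** Gray's test and a multistate Cox model for treatment. No sedation variable is named.
- **Clinical Instability (Protocol 7.3, 8.1.3, 8.2.3, Appendix B).** The RASS values used are -4, -5, +3 and +4. The line is not used.
- **Sedation target (Protocol 8.4.1).** The target is RASS 0. Both -2 and -3 lie below it and call for the same response.
- **Sedation summaries (SAP 4.7, 5.5.2, 6.2).** The line is used, descriptively.
- **Adjusted analyses (SAP 6.4).** The line is used through baseline sedation category, which is to be explored in addition to the four pre-specified covariates.

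Protocol 12.2 mentions a t-test for agitation scores without saying whether RASS is meant. The SAP's plan for these scores is descriptive, and I have followed the SAP.

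**The case against.** The strongest reply is that the procedure governs. Protocol 8.4.1 refers to the appendix for the procedure. Step 1 of that procedure refers back to the table only for agitation scores, while steps 2 and 3 define -1 to -5 in full without it. Someone who follows the steps scores movement without eye contact as -3. This stands, and it rules out the reading that staff will systematically shift patients into light sedation. The text supports only that they could. The table does come first and carries the descriptions, so the possibility remains.

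Exposure may also be small. Research personnel score only where no validated scale is routinely charted, and they may use SAS instead. SAP 5.5.2 says that each centre used whatever scale it had in use. This stands too: the documents do not show that any score came from the table.

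A reader might further infer a biased comparison between arms, since scoring is open-label. The documents do not support that. Randomization is stratified by site (Protocol 10.3.1, SAP 2.2), so both arms at a centre share its scoring source, and nothing suggests that raters resolve the ambiguity differently by arm. Open-label scoring means that a difference cannot be excluded, but none is shown.

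Finally, a corrected appendix may come too late. SAP 5.5.2 describes scoring in the past tense, the SAP cites web sources accessed in July 2024, and the Protocol synopsis plans enrolment to September 2021. Notifying sites would not change scores already recorded. This stands and shapes the remedy.

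**Conclusion.** The inconsistency is real and falls exactly on an analysis cut, but its reach is short. Scores read from the Appendix E table could move some patients from moderate-to-deep into light sedation. The affected centres are those where RASS was scored from that table; their number is unknown, and so is the share of scores near the line. The affected outputs are the descriptive sedation summaries and the exploratory baseline sedation covariate.

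It would be wrong to infer any effect on the primary result or on the Clinical Instability criteria, since neither uses the -2/-3 line. This is a minor point, worth making because it is cheap to correct. It assumes that the table rows stand in the protocol as they read here; they are complete and legible, so an extraction fault is unlikely.

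**What to change.** Reconcile the table's -2 row with the procedure text in Appendix E. The procedure is the natural anchor, because it gives a response to voice one score, with no overlap or gap between -1 and -3. If scoring is still under way, notify the sites that use the appendix.

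If scoring is complete, as appears likely, make the change in the SAP:

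- State in 5.5.2 which definition of -2 and -3 underlies the light versus moderate-to-deep split.
- Add one check of the sedation summaries and of the analysis adjusted for baseline sedation, either omitting centres that scored from Appendix E or merging -2 with -3.

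Omitting centres requires knowing which ones used the appendix, and the documents do not say whether this was recorded. If it was not, merging is the workable option. It applies directly only to RASS scores. For centres using SAS or VA-MAAS, the nearest equivalent is to combine the light and moderate-to-deep categories.

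The cost is a few lines of text and one small extra analysis, with some loss of patients or of resolution within that check.

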Appendix F: Sedation Agitation Scale (SAS)

Riker Sedation-Agitation Scale (SAS)[*Need to Verify/reconcile citation, likely Prospective evaluation of the sedation-agitation scale in adult ICU patients. Crit Care Med 1999;27:1325-1329.*]

Score	Term	Description
7	Dangerous Agitation	Pulling at ET tube, trying to remove catheters, climbing over bedrail, striking at staff, thrashing side-to-side
6	Very Agitated	Requiring restraint and frequent verbal reminding of limits, biting ETT
5	Agitated	Anxious or physically agitated, calms to verbal instructions
4	Calm and Cooperative	Calm, easily arousable, follows commands
3	Sedated	Difficult to arouse but awakens to verbal stimuli or gentle shaking, follows simple commands but drifts off again
2	Very Sedated	Arouses to physical stimuli but does not communicate or follow commands, may move spontaneously
1	Unarousable	Minimal or no response to noxious stimuli, does not communicate or follow commands

Procedure for SAS Assessment

1. Agitated patients are scored by their most severe degree of agitation as described
 2. If patient is awake or awakens easily to voice (“awaken” means responds with voice or head shaking to a question or follows commands), that’s a SAS 4 (same as calm and appropriate – might even be napping).
 3. If more stimuli such as shaking is required but patient eventually does awaken, that’s SAS 3.
 4. If patient arouses to stronger physical stimuli (may be noxious) but never awakens to the point of responding yes/no or following commands, that’s a SAS 2.
 5. Little or no response to noxious physical stimuli represents a SAS 1.
- This helps separate sedated patients into those you can eventually wake up (SAS 3), those who can't awaken but can arouse (SAS 2), and those you can't arouse (SAS 1).

1.1 Background and rationale

Patients with acute respiratory failure (ARF) require invasive mechanical ventilation (MV) to support their work of breathing and provide adequate gas exchange until they recover from their acute illness. Although clinicians aim to wean and liberate patients from MV as soon as patients are capable of breathing unsupported, MV itself may induce respiratory muscle weakness, [4, 5, 6] patient-ventilator dyssynchrony [7, 8] and necessitate the administration of sedative drugs, all of which have been associated with a prolonged duration of dependence on MV. Since prolonged invasive ventilation is associated with increased morbidity and mortality [9, 10, 11], a major goal is to minimize the duration of weaning and aim for the highest proportion of patients successfully liberated from MV [12]. Avoidance of respiratory muscle atrophy, patient-ventilator dyssynchrony, and heavy sedation may enable clinicians to achieve this goal. Ideally, minimizing respiratory muscle atrophy and patient-ventilator dyssynchrony should theoretically occur if the level of ventilator assistance is adjusted to target normal or reasonable levels of respiratory effort [7, 8, 13].

Proportional assist ventilation with load-adjustable gain factors is a mechanical ventilation mode (PAV+ mode) that delivers assistance to breathe in proportion to the patient's effort [14, 15]. The proportional assistance, called the gain, can be adjusted by the clinician to maintain the patient's respiratory effort or workload within a reasonable range. PAV+ mode is the only ventilation mode that allows measurement and targeting of a specific range of respiratory muscle activity by the patient [16]. Currently, pressure support ventilation (PSV) mechanical ventilation mode is the most common mode used after the acute phase of illness [17] and thus may be considered the standard of care for assisted breathing of patients during the recovery phase of acute respiratory failure [18]. Several small studies have shown short term advantages of PAV+ over PSV, including improved patient-ventilator synchronization, improved adaptability to changes in patient effort, and improved sleep quality [7, 12, 19, 20, 21, 22]. One randomized controlled trial (RCT) compared PAV+ mode to PSV over 48 hours and demonstrated it was better tolerated [23], but to date, there has been no large, multi-centre RCT comparing the two modes head-to-head to evaluate impact on clinically important, patient-centred outcomes. This study is poised to answer several research questions that have remained unanswered to date: (1) Does PAV+, set to maintain a workload of breathing within the normal range, decrease duration of MV and (2) improve other clinical outcomes compared to the current standard of care using PSV? (3) Do patients randomized to PAV+ receive fewer administered sedatives and/or antipsychotic medications than patients randomized to PSV, and (4) are pain/agitation/sedation/delirium scores different between patients on PAV+ vs. PSV? (5) In addition to mode of ventilation, do factors such as age. sex, frailty score, comorbidity index, severity of illness, prior duration of MV, prior SBT/extubation failure, work of breathing, sedation, or early mobilization, influence duration of weaning and weaning success?

1.2 Study Objectives and Hypothesis

The primary objective of this study is to determine if, for patients with acute respiratory failure, ventilation with PAV+, instituted early in the recovery phase and set to maintain a workload of breathing within the normal range, will result in a shorter duration of time spent on mechanical ventilation than ventilation with PSV. The secondary objective of the study is to determine if other clinically important outcome measures are better with PAV+ as compared to PSV. A third objective of the study is to determine if, in addition to mode of ventilation, factors such as age, sex, frailty score, comorbidity index, severity of illness, prior duration of MV, prior SBT/extubation failure, work of breathing, sedation, or early mobilization, influence duration of weaning and weaning success differently in the two arms.

The hypothesis is that critically ill adult patients supported with PAV+ early in the recovery phase of acute respiratory failure will have a shorter duration of MV compared to PSV.

1.3 Research Questions

1.3.1 Primary Research Question

The primary research question is whether ventilation with PAV+, instituted early in the recovery phase and set to maintain a workload of breathing within the normal range, will result in a shorter duration of time spent on mechanical ventilation compared to ventilation with PSV for patients with acute respiratory failure.

1.3.2 Secondary Research Questions

The secondary research question is to determine whether other clinically important outcome measures are improved with PAV+ as compared to PSV. The primary and secondary research questions will be addressed using both frequentist and Bayesian methods.

1.3.3 Post-hoc pre-specified Research Questions

An additional pre-specified post-hoc research question that was developed after the protocol is to determine if there is heterogeneity of treatment effect within the study cohort. This will involve identifying clinically relevant subgroups of patients using cluster analysis techniques.

2 Study Methods

2.1 Trial design

The PROMIZING study is a multi-centre, randomized, parallel assignment, open label clinical trial designed with a superiority framework. Neither the clinical team nor the study investigators will be blinded to the study intervention. The study statistician will be blind to the study arm. Allocation ratio is 1:1 to the two arms of the study. Patients randomized to the PAV+ intervention arm will follow a PAV+ ventilation protocol, where PAV+ is set to maintain respiratory muscle pressure within a target range of 5-10 cmH2O. Patients randomized to the PSV control arm will follow a PSV ventilation protocol, where PSV is set to maintain usual clinical parameters of respiratory rate and tidal volume. In both arms, patients who are not tolerating the assigned mode will be placed on assist/control ventilation, and in both arms, patients will undergo daily screening for readiness for liberation with protocolized spontaneous breathing trials.

2.2 Randomization

Each participant in this study will be randomized to either PSV or PAV+ in a 1:1 ratio in a centralized electronic data capture system called Medidata Rave (Medidata, USA). Participant allocation to treatment will be via variable block randomization with varying block sizes and stratified by site to minimize the likelihood of predicting the next procedure assignment. Randomization will be attained using computergenerated sequence methodology, ensuring that the randomization methodology and the generated allocation sequence are concealed from the investigator and participants.

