10.3 Randomization & Blinding**10.3.1 Randomization**

Participants will be randomized once eligibility is determined, by having satisfied all of the inclusion criteria and none of the exclusion criteria, have passed the Pressure Support Trial and either not meeting Weaning Criteria or failing the ZERO CPAP Trial or failing the SBT. Each participant in this study will be randomized to either PSV or PAV+ in a 1:1 ratio in Medidata RAVE.

Participant allocation to procedure group will be via variable block randomization with varying block sizes and stratified by site to minimize the likelihood of predicting the next procedure assignment. Randomization will be attained using computer generation sequence methodology, ensuring that the randomization methodology and the generated allocation sequence are concealed from the investigator and participants.

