12.2 Statistical Methods Analysis

Analysis will follow the intention-to-treat principle. Baseline data will be analyzed descriptively (e.g. mean and standard deviation, median and interquartile range, counts and percentages as appropriate). Time to extubation will be summarized by cumulative incidence curves with death treated as a competing risk and compared between groups with the Gray test. The treatment effect will be expressed as a hazard ratio with 95% confidence interval from a multistate generalization of the Cox model. Additionally, a cause-specific Cox model where death is treated as a censoring event will be fit for comparison. Patients with missing outcome data will be censored at last contact. The secondary outcomes of ventilator-free days will be compared between the groups by means of a Wilcoxon test. The treatment effect will be expressed as the difference in median ventilator free days along with a 95% confidence interval obtained by bootstrap methods. The time-to-event outcomes ICU discharge and hospital discharge present the same special challenge as the primary outcome because death is a competing risk. Furthermore, "survivor-only" analyses are an improper subgroup which further complicates interpretation. To mitigate these problems, cumulative incidence curves will be constructed that provide estimates of the outcome of interest, accounting for death. Cause-specific treatment effects will be given as hazard ratios with 95% confidence intervals from Cox models. Time-to-death will be analyzed using standard methods for survival data (Kaplan-Meier curve, log-rank test) and the treatment effect will be expressed as a hazard ratio with 95% confidence interval. Four of the secondary outcomes describe weaning difficulties in various ways. These also suffer from the competing risk of death and other improper subgroup issues. These outcomes will be looked at primarily from a descriptive perspective. The outcome, "requiring A/C" will be compared by a chi-square test (or Fisher's Exact Test) and treatment difference will be expressed as an odds ratio with 95% confidence interval.

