3.2 Handling of Incomplete Data

It is important to realize that the problem of incomplete data is distinct from ITT. The ITT philosophy is to attribute the available patient data to the group they were randomized to, irrespective of compliance to randomization. However, it is not possible to analyze data that you do not have. Therefore, we will begin with the complete case analysis. However, this analysis can be biased, although if missing data is minimal, less than 5% say, bias will be minimal and conclusions will not be affected by more sophisticated approaches.

There is controversy regarding the appropriateness of imputing outcome data in clinical trials. Therefore, even if loss to follow-up (i.e. missing outcome) exceeds 5% no imputation methods will be employed for post-randomization outcomes. The main value of imputation techniques is to enable an analysis to use all complete data. Some unpublished simulations developed by the statistician demonstrate that if the outcome is the only thing missing, even if missing at random, multiple imputation has virtually no effect on bias or precision. Furthermore, post-randomization outcome data is frequently not missing at random and other simulations conducted by the statistician show multiple imputation may not correct the bias incurred by data not missing not at random. Also note that since the primary analysis is a time-to-event analysis, no subjects are dropped from the analysis, they are simply censored if necessary. Multiple imputation may be employed to handle missing covariate data in secondary, adjusted analyses.

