6.1 Primary Outcome

The primary outcome of time to successful liberation from mechanical ventilation will be summarized using cumulative incidence curves with death considered to be a competing risk. Cumulative incidence will be compared across groups using Gray's test.

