6.1.1 Primary Analysis

Treatment effect will be reported as a hazard ratio with 95% confidence interval. The primary analysis will use a mutistate generalization of the Cox proportional hazard model. This approach simultaneously models the association between treatment and all transitions in the model. Missing outcome data will be treated as censored at the date of last contact.

PAV
PSV

Weaning Criteria
SBT/TMT
Extubation/Disconnection

Liberated, in ICU

ICU Discharge

Liberated, in hospital

Hospital Discharge

Liberated, home

Death

Dead

Figure 3: State transition diagram

Figure 3: State transition diagram

IMV = invasive mechanical ventilation; SBT = spontaneous breathing trials; TMT =tracheostomy mask trials; ICU = intensive care unit

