6.1.2 Secondary Analyses

A secondary analysis will be performed using a cause-specific Cox model to model the treatment effect on successful liberation with death prior to successful liberation treated as a censoring event.

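### The frequentist liberation analyses name neither site, the only randomization stratum, nor the four SAP 6.4 covariates; they are valid, but they may forgo precision, and the announced adjusted analysis has no fixed model

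*SAP*

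**What the plan says.** Protocol 10.3.1 specifies "variable block randomization with varying block sizes and stratified by site", and SAP 2.2 repeats it: allocation is "stratified by site to minimize the likelihood of predicting the next procedure assignment". No other stratum is named.

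For the primary outcome, SAP 6.1 states: "Cumulative incidence will be compared across groups using Gray's test". SAP 6.1.1 takes the HR from a multistate Cox model: "This approach simultaneously models the association between treatment and all transitions in the model". Protocol 12.2 agrees: "The treatment effect will be expressed as a hazard ratio with 95% confidence interval from a multistate generalization of the Cox model". SAP 6.1.2 adds: "A secondary analysis will be performed using a cause-specific Cox model to model the treatment effect on successful liberation". None of these sections names a site term or a baseline covariate.

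SAP 6.4 lists four covariates of particular interest: duration of ventilation before randomization (in days and also as a split at 5 days), the reason for not being ready to extubate (failed SBT, CPAP-zero trial or weaning criteria), failed extubation, and frailty. It then says "we will explore the effects of baseline cumulative fluid balance and baseline sedation category in adjusted analyses". SAP 3.2 says "Multiple imputation may be employed to handle missing covariate data in secondary, adjusted analyses". SAP 7 adjusts the Bayesian analyses, including time to liberation, for the covariates of interest, but points to section 3, which is Statistical Principles; the list is in 6.4. The Bayesian models do not name site either.

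**The concern.** When randomization is stratified, an analysis that ignores the stratum gives standard errors that are too large if the stratum is prognostic. Omitting prognostic baseline variables also costs power in a Cox model.

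The documents treat some of these variables as possibly prognostic. Protocol 12.2 links more than 5 days of prior ventilation to prolonged weaning. SAP 1.1 asks whether frailty, prior ventilation and prior SBT or extubation failure influence weaning duration. (SAP 1.2 is weaker support, because it asks whether these influences differ between arms.)

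Two things are at stake. One is precision available from baseline data that are collected anyway. The other is that adjusted frequentist analyses are announced without a fixed outcome, model, covariate set or handling of site. SAP 2.6 requires an unplanned label only for supporting post-hoc analyses that the SAP does not identify, so an analysis that is announced but left open escapes that label. Also, with no matching adjusted frequentist model, a difference from the Bayesian result could come from the prior, the model family or the adjustment.

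**Working it through.** **1. The plan's own figure.** Inputs (Protocol 12.1, SAP 2.3): two-sided alpha 5%, power 80%, HR 1.30, PSV median 7.70 days, 1:1 allocation, death as censoring.

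- Events = 4(z₀.₉₇₅ + z₀.₈₀)² / (ln HR)² = 4(1.960 + 0.842)² / 0.2624² = 456.1. The plan states 456.
- Liberation hazards: ln 2/7.70 = 0.0900 per day on PSV and 0.0900 × 1.30 = 0.1170 on PAV+. The death hazard is not printed. Solving this row of the table gives 0.0163 per day, which reproduces seven other rows within 1 patient.
- Event probability λ/(λ + 0.0163) is about 0.846 and 0.878, mean 0.862. Then 456/0.862 = 529, as stated.
- 529/0.95 = 556.8, so 557, or 558 with equal arms.

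The sizing is an unadjusted two-group comparison with no term for site or covariates.

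**2. Simulation.** The documents give no number of sites, block sizes, site variance or covariate strength. The following are therefore assumptions, not properties of this trial:

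- 529 patients in 20 unequal sites, with blocks of 2, 4 and 6 within site.
- Hazard λ₀·exp(β·arm + covariates + site), with Gaussian site effects and log-hazard SD 0 to 0.5 for site and 0 to 0.5 for the four covariates combined.
- Death at 0.0163 per day and censoring at day 90.
- β set so that the marginal HR is 1.30. The conditional HR is then 1.346 at SDs 0.3/0.3 and 1.411 at 0.5/0.5.

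The models were unadjusted Cox, Cox with site frailty, and Cox with site frailty plus 7 covariate degrees of freedom (spline 2, weaning status 2, failed extubation 1, frailty 2). If the liberation transition has its own baseline hazard and coefficients, its partial likelihood is the same as that of the cause-specific Cox model, so the results carry over to that part of SAP 6.1.1. With no heterogeneity, the mean number of events was 456 and power was 80.3%.

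**3. Rejection under the null.**

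- Unadjusted: 4.9–5.1% at site SD 0, 4.1–4.7% at 0.3, 3.3–4.1% at 0.5.
- Frailty plus covariates: 5.0–5.6%, mean 5.3% (Monte Carlo range ±0.15).

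**4. Power (%), size-matched**, each test at its own simulated 5% critical value (Monte Carlo range about ±1.0):

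| Site SD / covariate SD | Unadjusted | Site frailty | Frailty + covariates | Gain, site | Gain, both |
|---|---|---|---|---|---|
| 0 / 0 | 80.6 | 80.3 | 79.2 | -0.3 | -1.4 |
| 0.3 / 0 | 83.4 | 84.5 | 83.7 | +1.1 | +0.3 |
| 0.5 / 0 | 86.9 | 90.0 | 89.2 | +3.1 | +2.3 |
| 0 / 0.3 | 78.3 | 78.3 | 82.8 | 0.0 | +4.5 |
| 0.3 / 0.3 | 81.0 | 81.9 | 86.2 | +0.9 | +5.2 |
| 0 / 0.5 | 78.9 | 78.8 | 90.0 | -0.1 | +11.1 |
| 0.5 / 0.5 | 84.2 | 86.1 | 93.8 | +1.9 | +9.6 |

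At the nominal 5% level the gains are 0 to about 7 points for site and -0.3 to +12.5 for both, partly because the unadjusted test is conservative there. At 0.3/0.3, size-matched power is 81.2, 82.0 and 85.7 with 12 sites, and 81.9, 83.5 and 86.4 with 30.

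**5. Other calibration.** A second simulation (558 patients, 23 sites) fixed the conditional HR at 1.30.

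- Covariate SD 0.3, no site effect: unadjusted power 76.4%, covariate-adjusted 81.8%.
- No site or covariate effect: full stratification by site lowered power from 80.5% to 75.7%.
- Unadjusted size at site SD 0, 0.3 and 0.5: 5.0%, 4.3% and 3.7%, the same pattern as in step 3.

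Not simulated: Gray's test, the other transitions, tied times (times are recorded to 0.1 day), missing covariates and imputation.

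**The case against.** The strongest reply is that the plan has made a legitimate choice. SAP 3.2 places adjustment among secondary analyses, the unadjusted test is valid, and the marginal HR is what the trial was sized for. That stands: a conditional primary HR is an option and not a correction.

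It also stands that site alone adds little, that the sentence on stratification gives predictability of allocation as its reason and does not call site prognostic, and that every gain rests on assumed SDs. The improvement applies to Cox models only, so an unadjusted Gray's test would sit beside an adjusted HR, and the plan has no rule for disagreement.

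Finally, the risk of choosing a model after seeing data is limited. The primary tests are fixed, the statistician is blind to arm (SAP 2.1), analysis waits for SAP approval (SAP 2.6), and SAP 6.3 and 6.4 speak of exploration.

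This does not settle which frequentist adjusted model will be run. SAP 6.4 leaves the coding of prior ventilation open, and no section says whether the covariates enter together or how site is handled.

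**Conclusion.** The point holds as a matter of efficiency and specification. A reader might infer more, and the documents do not support these readings:

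- *The analysis is invalid because it ignores the stratum.* The unadjusted Cox test holds its level and errs on the conservative side when sites differ.
- *The trial is underpowered as a result.* Cox power stays near 80% if 1.30 is the marginal HR. It falls below that if 1.30 is conditional and the covariates matter, but the sizing uses marginal medians.
- *No liberation analysis adjusts for covariates.* The Bayesian one does, so the omission is limited to the frequentist analyses.
- *The primary result is open to model selection.* Only the secondary adjusted analysis is.

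Under the stated assumptions, moderate heterogeneity (0.3/0.3) gives about 5 size-matched points for site plus covariates and about 1 for site alone. The gains near 10 need a combined covariate SD of 0.5. If nothing is prognostic, about 1 point is lost. Confidence in the size is moderate, because the prognostic strengths are assumed.

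**What to change.** **SAP 6.1.1, liberation transition, and likewise SAP 6.1.2:** add site as a shared frailty and the four SAP 6.4 covariates. Avoid full stratification by site, and fixed effects across many small sites. Enter prior ventilation as continuous with a restricted cubic spline, which SAP 6.5 already allows for the subgroup analysis. Extend the SAP 3.2 covariate imputation to this model. Label the HR conditional, report the unadjusted marginal HR, cumulative incidence curves and Gray's test beside it, and state in advance which result is the primary inference.

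**If the unadjusted HR stays primary:** name this exact model in SAP 6.1.2 as the single adjusted frequentist liberation analysis.

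**SAP 7:** change the covariate pointer from section 3 to section 6.4.

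**Cost:** SAP wording and model terms, with no new data. The liberation model has 8 coefficients (treatment plus 7) and one site variance, so 456/8 = 57 planned events per coefficient. The downsides are:

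- the HR becomes conditional;
- size is slightly above nominal, about 5.3%, and likelihood-ratio and score tests do not remove this;
- rules for small sites and missing covariates are needed;
- about 1 point of power is lost if nothing is prognostic.

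Site effects are not proposed for death before liberation. At most 529 − 456 = 73 planned patients lack a liberation event, which is under 4 per site if there are 20 sites.
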